#### **ASSESS KIOS-BIPOLAR OR eMOODS:**

- a. At the beginning of the study subjects will be provided preformatted evaluation sheets and will be encouraged to note observations regarding ease/benefits of use, impediments to use, and suggestions for additional features that would enhance the utility of KIOS-Bipolar or eMoods for sustained health.
- b. We will ask the subjects to estimate how completing the KIOS-Bipolar /eMoods assessments contributed to their self-awareness, attitude, and overall sense of satisfaction with their health status.
- c. We will assess the sensitivity of KIOS-Bipolar to identify improving or worsening by comparing the concordance between subject-assessed items with staff -administered BISS items that address similar symptoms.

**Plan of analysis:** The primary aims of the analyses are to investigate patterns of adherence and attrition. The term adherence refers to the extent to which participants follow the weekly completion of KIOS-Bipolar's eight pivotal symptoms of bipolar disorder. Adherence will be measured through such usage indicators as the proportion of weeks completed on time, the proportion completed only with follow-up prompts, and the number of weeks not submitted. Proportions of stable trajectories or improving trajectories are of primary interest. With  $n=90$  subjects (which allows for as many as 30 of the enrolled 120 subjects to have met some criterion for early termination) in the study we will be able to estimate any proportion within 0.10 with 95% confidence. For proportions larger than 0.9 we will be 95% confident we are within 0.06 of the true proportion. For a trajectory neither improving nor degrading there should be a 0.5 proportion

UTHSCSA tracking number: HSC20150321H

of each. For any hypothesis test for a proportion improving or degrading, i.e. not 0.5, we have 0.80 power at two tail significance of 0.05 to detect 0.65 different from 0.5 with n=90 subjects. For subgroups of patients with n=45 we can detect 0.71 different from 0.5 and with n=30 we can detect 0.74 different from 0.5. When comparing proportions of two subgroups of subjects, we will be 95% confident that the difference in proportions of the two subgroups is less than 0.25 for subgroups of n=30 and smaller than 0.20 for subgroups of size 40. If the proportions are larger than 0.9 (i.e. less variable), then we will be 95% confident that the difference in proportions of two subgroups with n=30(45) is less than 0.15 (0.12).

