Assumptions needed for each analysis will be examined to assure they are reasonably well met and the conclusions are valid. End of study overall improvement or not for each measure can be analyzed with logistic regression using covariates and predictors of interest. By focusing analyses on proportions and changes in trajectories, each subject will serve as their own control and trends in improved scores, symptoms and behavior may be identified.

Initially, we will also assess the effects of site, ethnicity, and bipolar disorder subtype (BD I, BD II), but none of these factors will be retained in the final model if they are not shown to be significant moderating factors.

The rate of dropout at any given time will be modeled through logistic regression models, with health, socioeconomic, and treatment factors as explanatory variables. *The impact of quality of life on dropout will be assessed similarly.*

**Outcome Measures from KIOS Analytics:** Knowledge Base performance metrics will be computed to measure the effectiveness of the content provided to patients. These metrics take several forms and are based on changes in the symptom scores for all subjects in the field trial (see Phase I Final Report). Changes in the symptom scores provide a global measure of efficacy. Each of these measures can be computed as a function of changes, either over the course of the entire field trial or at each incremental assessment. This latter approach will provide a measure of effectiveness over time. Other KIOS analytic methods will reveal which specific content in the knowledge base needs improvement. Behavioral frequency analysis will show which patient states are entered most frequently. Behavioral transition analysis will show which conditions are precedents to undesirable states.

**Implementation of Clinical Trial Results into Final Product:** The results of the randomized trial will be used to make further refinements to KIOS-Bipolar. The KIOS-generated results will be used to guide changes to the knowledge base. Suggestions about additional features will be considered in development of the commercialization plans.

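### The only regression model named for clinical outcomes reduces each measure to end-of-study improvement or not, leaving score grading and intermediate visits out of any stated between-arm analysis

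*Combined protocol and SAP*

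**What the plan says.** In the Plan of analysis (under the heading on assessing KIOS-Bipolar or eMoods), the sentence on clinical outcomes is "End of study overall improvement or not for each measure can be analyzed with logistic regression using covariates and predictors of interest". Neither a threshold for improvement nor a reference visit for someone who stops early is given. The next sentence reads, in part, "By focusing analyses on proportions and changes in trajectories, each subject will serve as their own control". The same section puts stable or improving trajectories among the quantities of primary interest. The paragraph on KIOS analytics allows symptom-change measures at each assessment. None of this text names a model that compares the randomised arms.

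The data are richer than the model. Table 1 and objective f schedule the BISS-42 at weeks 0, 8, 16, 24, 32, 40 and 52, and the text below Table 1 describes BISS items scored 0 to 4. Table 1 schedules the LFQ at weeks 0, 8, 16 and 52. Hypothesis a in section C predicts that the KIOS-Bipolar arm will do better on proportion of time in clinical states and on LFQ scores.

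On attrition, the planning sample of 90 is one "which allows for as many as 30 of the enrolled 120 subjects to have met some criterion for early termination". The Early termination paragraph in section B lists BISS suicide, depression and mania scores among the criteria. Dropout is to be modelled by logistic regression, but no rule is given for the clinical outcomes of those who drop out.

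**The concern.** A yes/no outcome treats a large and a trivial improvement alike, and a single end-of-study value leaves most of the follow-up unused. In a trial of 120 people, the power lost this way matters for the effectiveness hypothesis. The undefined cut-off also means that improvement could be defined after the data are seen.

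Missing outcomes are the second problem. Because termination depends partly on the BISS scores themselves, the people without a week-52 value are likely to include those who worsened. If they are left out of an end-of-study analysis, the arms are compared in a group selected on outcome.

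**Working it through.** **1. The plan's own power figure.** The plan states "we have 0.80 power at two tail significance of 0.05" "to detect 0.65 different from 0.5 with n=90 subjects". This is a one-sample test of a proportion against 0.5. By the normal approximation, power = Φ{(|p − 0.5| − 1.96√(0.25/n)) / √(p(1 − p)/n)}. For n = 90 and p = 0.65 this is Φ{(0.15 − 0.1033)/0.0503} = 0.82; the exact binomial test gives 0.81 and the continuity-corrected version 0.79. For n = 45 and p = 0.71 the three results are 0.83, 0.79 and 0.78. For n = 30 and p = 0.74 they are 0.78, 0.77 and 0.71, slightly short of 0.80. The planning size also checks: 90/(1 − 0.25) = 120. So the figures broadly reproduce, but they say nothing about the power to compare two arms. With 45 per arm and 50% improved in one arm, 80% power needs about 78% improved in the other.

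**2. Visits unused by the end-of-study model.**
- BISS-42: six post-baseline visits less week 52 = five (weeks 8, 16, 24, 32, 40).
- LFQ: three post-baseline visits less week 52 = two (weeks 8, 16).

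**3. Information lost by dichotomising.** Assumption: normal outcome. Splitting so that a share p counts as improved has relative efficiency φ(c)²/[p(1 − p)], where c is the p-quantile of the standard normal. The documents give no improvement rate, so a range is shown.

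| Share improved | φ(c)² | p(1 − p) | Efficiency | Loss |
|---|---|---|---|---|
| 50% | 0.1592 | 0.2500 | 0.637 | 36% |
| 65% | 0.1372 | 0.2275 | 0.603 | 40% |
| 80% | 0.0784 | 0.1600 | 0.490 | 51% |

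The 36% at an even split is the smallest loss.

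**4. Power between arms.** Assumptions: 1:1 allocation (no ratio is stated), 45 per arm (90/2), two-sided 0.05, 50% improved in the comparator arm, no covariates. The score is compared by t-test. The binary outcome is compared as 0.5 against Φ(d), with power Φ{(Φ(d) − 0.5 − 1.96·SE₀)/SE₁}, where SE₀ is the pooled and SE₁ the unpooled standard error.

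| Effect d | Φ(d) | SE₀ | SE₁ | Power, score | Power, yes/no |
|---|---|---|---|---|---|
| 0.5 SD | 0.691 | 0.1035 | 0.1015 | 0.65 | 0.46 |
| 0.6 SD | 0.726 | 0.1027 | 0.0999 | 0.80 | 0.60 |

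Put another way, the effect that gives 80% power on the score with 45 per arm is (1.96 + 0.8416)√(2/45) = 0.59 SD. To detect it as yes/no would take 75, 87 or 121 per arm if 50%, 65% or 80% of the comparator arm improve. Under 1:1 allocation the trial enrols 60 per arm.

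**5. Gain from averaging visits.** Assumptions: the same correlation r between every pair of visits including baseline, and complete data. The ratio of the variance of the baseline-adjusted mean of six BISS visits to that of a baseline-adjusted week-52 value is [(1 + 5r)/6 − r²]/(1 − r²).
- r = 0.5: (0.583 − 0.250)/0.750 = 0.44
- r = 0.7: (0.750 − 0.490)/0.510 = 0.51

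This applies only to the visit-averaged arm difference. A week-52 contrast from a model with arm-by-visit terms would, with complete data, have essentially the variance of an ordinary adjusted week-52 comparison.

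**The case against.** The strongest reply is that the wording is permissive: the logistic analysis *can be* done, and the plan also speaks of trajectories and of measures at each assessment. It further says that adherence and attrition are its primary aims, and its clinical construct is categorical (seven states). All of that stands, and it rules out saying that the plan confines itself to a single dichotomy. It does not fill the gap, because none of the other analyses comes with a between-arm model, and hypothesis a compares LFQ scores between arms.

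A reader might also infer that early terminators are excluded and that the comparison is therefore completers-only. The documents do not say so. The figure of 90 is a planning allowance, not an analysis set; the end of study could mean the last visit for someone who stops; and dropout is itself modelled. What can be said is that no rule exists, and that leaving these participants out would select on outcome.

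It is fair, too, that no between-arm hypothesis names a continuous BISS-42 total, and that a repeated-measures model of BISS-42 would test neither LFQ nor time in remission. The fix has to cover LFQ and leave time in state to a separate comparison.

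**Conclusion.** The concern holds in a limited form. The only regression model named for clinical outcomes dichotomises graded scores at one time point, with no cut-off, no stated between-arm use of the intermediate visits, and no rule for the outcomes of up to 30 of 120 participants (25%). The cost is a 36% to 51% loss of information for improvement rates of 50% to 80%, and a fall in power of about 0.2 at effects of 0.5 to 0.6 SD (0.65 − 0.46 = 0.19; 0.80 − 0.60 = 0.20). These sizes rest on the assumptions stated with the calculations. The effect sizes, improvement rates and visit correlations are illustrative, since the documents supply none.

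It would go too far to read the 0.44 to 0.51 variance ratio as the general benefit of a repeated-measures model. It belongs to one contrast under restrictive assumptions.

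**What to change.** Prespecify the between-arm analysis of LFQ scores, and of BISS-42 depression and mania scores, as a mixed model for repeated measures on all post-baseline visits (weeks 8, 16 and 52 for LFQ; weeks 8 to 52 for BISS-42). Include arm, visit, arm-by-visit, baseline score and site. Include all randomised participants, with the visits they made before termination.

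Name the contrast in advance: the visit-averaged arm difference, with the week-52 difference also reported. State that the model assumes missing scores are explained by the observed data it contains, and say how outcomes after termination are to be regarded. Keep the logistic analysis as supportive, with improvement defined by a stated threshold and visit.

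Time in clinical states (hypothesis a) still needs its own between-arm comparison, which this model does not provide.

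The cost is a little more analysis work and no new data. The visit-averaged contrast answers a slightly different question from week 52 alone, which is why both should be reported.

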**Table 1. Schema for Randomized Clinical Trial**

Week	0	1-7	8	9-15	16	17-51	24, 32, 40	52	RS
MINI-6.0, Demographics/course of illness	X								
K-TABS/eMoods	X	X	X	X	X	X		X	
Life Functioning Questionnaire	X		X		X			X	
BISS-42,	X		X		X		X	X	
BISS Self-Assessment	X		X		X		X	X	X
KIOS NIH Software Evaluation Form					X			X	

The clinician administered scale will be the 42 item Bipolar Inventory of Symptoms Scale (BISS), however comparisons will be limited to the symptom areas represented in both K-B and eMoods, e.g., depression and mania subscales; depression, mania, irritability and anxiety domains. The BISS Self (BISS-S) is a 27item scale covering similar symptoms to the BISS, but answered as yes/no, rather than the 0-4 range of the BISS. The MINI is a structured diagnostic interview providing current and lifetime psychiatric diagnoses, requiring approximately 20 minutes.

g. Estimate the utility of ancillary features of Kios-Bipolar or eMoods. These features include capability to submit to the investigative staff displays of symptom trajectories for the patient's medical record and visual displays of selected aspects of the patient's illness/wellness. No transmission of data to treating clinical staff will occur as component of this study.

h. Assess sensitivity of K-B assessed improvement or worsening by comparison with assessment by BISS-Self and BISS-42.

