**Inclusion Criteria:**

1. Male or female outpatients 18 years of age or older
2. Bipolar I or II disorder as assessed by MINI 6.0
3. In psychiatric outpatient treatment at UTHSCSA, University of Louisville, or Lindner Center of Hope, Mason Ohio
4. Currently taking mood stabilizer or second generation antipsychotic for 4 weeks or longer
5. Ability to access Kios-Bipolar or eMoods (via computer, smartphone or tablet)

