It should be noted that the Summary Statement contained a criticism that email reminders prior to expected assessment days would be a direct intervention that confounds weekly reporting adherence. Because the reminder will be sent *after* the scheduled assessment day, we are still able to judge adherence to the study schedule; the response to the notifications will provide a relevant secondary outcome measure. In addition, many subjects in the Field Trial requested this feature, which will almost certainly be included as an option in the commercialized version of KIOS-Bipolar.

Study participants assigned to eMoods will also have the software downloaded on their device (Either Android phone or computer) and the procedure of demonstrating the software and providing contact information described above will be followed. In the case that the IOS version of eMoods is not available by the time the study begins, the randomization of subjects will be stratified by device to ensure equal representation in the treatment groups.

Participation in the study will not impact the patient's routine clinical care for his/her bipolar condition. However, some subjects may want to discuss their KIOS-Bipolar or eMoods experience with their psychiatrist and/or psychologist, and will be permitted to do so.

Participants randomized to their assigned group who are unable to complete their weekly entries based on the following criteria: technical difficulties completing the weekly entry, difficulty emailing data to Research Coordinator (for eMoods group), and any other technical issues that may arise throughout the course of the study will have the option to switch to the other group. The participants who have been switched to the other group will have to complete a BISS self-report form along with a weekly entry from the newly assigned group.

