### ***b. Sources of Materials***

- Individuals enrolled into the study will be assigned study password-protected ID numbers.
- All information obtained from human volunteers will be utilized strictly for research purposes.

UTHSCSA tracking number: HSC20150321H

Information to be collected includes: demographic data, MINI-6.0, self-reported symptoms via the KTABS or eMoods (i.e., online questionnaire), Life Functioning Questionnaire, BISS and subjective information regarding the user experience with the software.

- Information will be collected, handled and stored according to the HIPPA regulations and study participants will be asked to read a Privacy Notice and sign a Research Authorization (HIPPA consent). Study participants will be given a copy of the signed consent form for his/her records.

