### ***e. Protections Against Risk***

Minimal risk to subjects or subject's privacy is anticipated. Nonetheless, we recognize the need for strict protection of confidentiality in this study. To address this, records of patients will be retained as required by statute in locked files. All computer files will be password protected. Subjects will be identified in common-use computer files by ID number only. Research reports and publications will report only group data and not individual names. Identities of subjects will not be revealed in the publication or presentation of any results from this project. All investigators and research staff at the respective institutions have completed the requirements for human research subjects' protection. All investigators and research staff at BDC have completed the requirements for human subjects' protection. The study will be performed in accordance with HIPPA regulations and approved by the IRBs at the UTHSCSA, the University of Louisville and the University of Cincinnati.

Participation in the study will be terminated if a patient has a score of 4 on the BISS suicide item, BISS Depression Scale  $\geq 50$ , or BISS Mania Scale  $\geq 35$ , or if the treating psychiatrist determines that a patient poses an imminent risk of self-harm.

All subjects enrolled in the trial will have been under care of a psychiatrist at their respective institutions prior to enrolling in the study. All subjects will continue to receive evidence-based care provided by outstanding psychiatrists at the three sites. Participation in the study will not impact the patient's routine clinical care for his/her bipolar condition. The study's planned visits will generally be scheduled to coincide with the patient's regularly scheduled clinic visits both for convenience and in order to not interfere with regular care.

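### The KIOS analytics and the one-sample tests against 0.5 read uncontrolled symptom change as app effectiveness, although drug treatment may change freely for 52 weeks and no recording of those changes is described

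*Combined protocol and SAP*

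**What the plan says.** **Efficacy reading.** Under Outcome Measures from KIOS Analytics, the knowledge-base metrics are meant to show how effective the content given to patients is. They are computed from changes in symptom scores, and the text adds: "Changes in the symptom scores provide a global measure of efficacy". It names neither a comparator nor an adjustment for drug treatment. The next paragraph uses the KIOS results to guide changes to the knowledge base.

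**One-sample tests.** The Plan of analysis makes stable or improving trajectories a primary interest. It takes 0.5 as the value expected when nothing is changing, and claims 0.80 power to detect 0.65 at n=90. Participants are described as their own controls.

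**Drug treatment.** Inclusion criterion 4 reads: "Currently taking mood stabilizer or second generation antipsychotic for 4 weeks or longer". No dose-stability rule follows. Under Protections Against Risk, "All subjects will continue to receive evidence-based care provided by outstanding psychiatrists at the three sites" and "Participation in the study will not impact the patient's routine clinical care for his/her bipolar condition". Section D (Software) adds that "some subjects may want to discuss their KIOS-Bipolar or eMoods experience with their psychiatrist and/or psychologist", which is permitted.

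**Data.** Sources of Materials states: "Information to be collected includes: demographic data, MINI-6.0, self-reported symptoms via the KTABS or eMoods (i.e., online questionnaire), Life Functioning Questionnaire, BISS", followed by user-experience information. The nearest row in Table 1 is "MINI-6.0, Demographics/course of illness", at week 0 only. Neither place has a medication item after baseline.

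**Randomized comparison.** Hypotheses a, e and g compare the two arms on time in clinical states, LFQ scores and symptom-score changes.

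**The concern.** Symptom change in a treated, episodic illness has several causes besides an app: response to a drug that may have been started only four weeks before entry, later drug changes, regression to the mean and natural course. A within-subject metric credits or debits all of them to KIOS-Bipolar. A participant whose drug is changed and who then improves counts as evidence that the advice works. One who worsens, and whose drug is changed for that reason, counts against it.

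Two things are at stake. The content metric may support an efficacy statement that the data cannot carry, and it feeds into revision of the product. Separately, if the randomized arms differ, nobody will be able to describe how far prescribing differed between them.

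**Working it through.** **1. Reproduce the plan's figure.** Inputs from the Plan of analysis: n=90, two-sided alpha 0.05, null 0.5, alternative 0.65.
- Exact binomial: the smallest r with P(X ≥ r | 90, 0.5) ≤ 0.025 is r = 55. The upper tail is 0.022 and the two-sided level 0.045. Power = P(X ≥ 55 | 90, 0.65) = 0.812.
- Normal approximation with null variance: Φ(0.15/√(0.25/90) − 1.96) = 0.812.

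The stated 0.80 is reproduced, so the arithmetic is not the problem.

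**2. What the null means.** A true proportion of 0.5 corresponds to no app effect only if nothing else moves symptoms. The documents do not secure that: treatment is universal, may change, and no follow-up record of changes is described.

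**3. How far other causes could move the proportion (assumptions).** Suppose half the participants have a drug change, 50% of those without one improve, and the app does nothing.
- If 60% of changers improve: 0.5×0.50 + 0.5×0.60 = 0.55.
- If 70%: 0.5×0.50 + 0.5×0.70 = 0.60.
- If 80%: 0.5×0.50 + 0.5×0.80 = 0.65.
- If changes mostly follow worsening and 40%, 30% or 20% of changers improve, the same formula gives 0.45, 0.40 or 0.35.

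The documents give no rates, so this shows a range and is not a forecast.

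**4. Consequence for the test, app effect nil.** Probability of declaring improvement, P(X ≥ r | n, p), with r = 55 at n=90 and r = 30 at n=45:

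| True proportion improving | n=90 | n=45 |
|---|---|---|
| 0.50 | 0.022 | 0.018 |
| 0.55 | 0.145 | 0.076 |
| 0.60 | 0.460 | 0.225 |
| 0.65 | 0.812 | 0.475 |

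By symmetry, true values of 0.45, 0.40 and 0.35 give the same probabilities of declaring worsening.

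**5. Which n applies.** The n=90 is all 120 enrolled less 30, so it pools both arms. One arm would have about 45 (1:1 assumed; the ratio is not stated), where the plan's detectable proportion is 0.71. The plan does not say whether the KIOS metrics use this test, so both sizes are shown.

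**6. The randomized contrast.** If other causes move both arms equally, a between-arm test keeps its nominal 0.05 level. With 45 per arm, its power for 0.65 against 0.50 is 0.30, and 0.80 power needs about 0.78 against 0.50.

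**The case against.** **The trial is randomized.** A reader might infer that drug and app effects cannot be told apart anywhere in the study. The documents do not support that. Randomization balances entry medication in expectation, and hypotheses a, e and g are between-arm. That contrast estimates the total effect of being assigned the app, including any drug changes the app prompts. Potential Benefits even expects treatment to be optimized through the app's recommendations, so such changes may be part of the effect. This objection stands, and it confines the point to the KIOS analytics and the one-sample tests. Two gaps remain: the content metric names no comparator, and a between-arm difference could not be described in terms of prescribing.

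**The data lists may be incomplete.** A reader might infer that medication is not collected at all. The list in Sources of Materials is introduced as inclusive, the case report forms are not shown, and on-site monitoring requires source documentation of eligibility, which covers entry medication. This stands for baseline. The firm statement is that no collection of changes during follow-up is described. The treatment factors in the dropout model are undefined and do not fill that gap.

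**Objective d.** A reader might take its remark that comparison with eMoods is infeasible as proof that symptom change has no comparator. It concerns satisfaction with clinical information only, and hypothesis g does compare symptom changes between arms.

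**The metrics may belong to the earlier study.** The section refers to the field trial and the Phase I report. That ambiguity is real. However, the section is written in the future tense and is followed by a paragraph on using the randomized trial's results, so the metrics appear intended for this study too.

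**Unrestricted care is a design choice.** It suits an effectiveness study and is not criticised here.

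**Conclusion.** The point holds for the KIOS analytics and the one-sample tests against 0.5. As written, they attribute to the app whatever moves symptoms over 52 weeks. Under the assumed drift to between 0.55 and 0.65 with no app effect, the chance of declaring improvement rises from about 0.02 to between 0.145 and 0.812 at n=90, or between 0.076 and 0.475 at n=45. The size depends wholly on that assumed range, and the direction is not known.

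It does not extend to the randomized contrast as an estimate of total app effect, although the open design and the option to switch groups weaken that contrast in other ways. Nor is differential prescribing shown. It is possible, because discussion with psychiatrists is allowed in both arms and Potential Risks says that evidence of worsening will be passed to the treating clinician. The plan could not detect it.

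**What to change.** 1. **Relabel the metrics and tests.** In Outcome Measures from KIOS Analytics, replace the effectiveness and efficacy wording with *describe symptom change under usual care plus KIOS-Bipolar*, and state which participants and arm the metrics cover. In the Plan of analysis, say that the one-sample tests against 0.5 describe change and do not measure app effect.
2. **Rest effectiveness claims on the randomized comparisons** already named in the hypotheses: time in clinical states, LFQ and symptom change, using the BISS-42 and BISS-Self that both arms complete. LFQ should stay in, since it is a named outcome collected in both arms.
3. **Record psychotropic medication changes** (drug; started, stopped or changed; date) from the clinic record in both arms at weeks 0, 8, 16, 24, 32, 40 and 52, and report them by arm. Do not adjust the main between-arm comparison for them: they arise after randomization and may be part of the app's effect.
4. **Reconcile two passages.** Objective g, below Table 1, says that no data go to treating staff as part of the study. Potential Risks says that evidence of worsening will be conveyed to the psychiatrist or therapist. That route could itself lead to treatment changes.

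The cost is some rewording, one short form taking a few minutes at visits that already occur, and a less favourable product claim. The sponsor must also accept the limited power of the between-arm comparison shown in step 6. Because participants are treated at the study sites, the clinic record should be at hand. Changes not captured as they occur are harder to reconstruct later.
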